## 5. TREATMENT OF SUBJECTS

### 5.1 Investigational treatment

#### Intervention group:

The intervention consists of performance of pre-trained Slow PACE breathing by the patient at induction of anesthesia for breast cancer surgery.

#### *Slow PACE breathing*

Slow PACE breathing is a simple technique of deep belly breathing in a low frequency (0.1 Hz = 6 breaths per minute), performed in supine position, synchronizing the breath with a breath pacer provided by an audio-guide.

#### *Training*

Patients will be trained pre-operatively in the Slow PACE breathing technique using an instruction video combined with a personal instruction by video-call.

Thereafter patients are requested to practice Slow PACE breathing once daily for at least 5 minutes using a provided audio-guide, which patients can listen on their portable device (e.g. phone, tablet or laptop).

### 5.2 Use of co-intervention

Patients in both groups will not receive pre-medication with a benzodiazepine (e.g. oxazepam).

## 6. INVESTIGATIONAL PRODUCT

No investigational product or treatment is used in this study.

## 7. NON-INVESTIGATIONAL PRODUCT

No investigational product or treatment is used in this study.

## 8. METHODS

### 8.1 Study parameters

#### 8.1.1 Main study parameter

Anxiety scored by Spielberger's State Anxiety Inventory (STAI-S)

#### 8.1.2 Secondary study parameters

- Mean arterial pressure (MAP) just before induction
- Total dose of hypnotics (propofol in milligrams) needed for induction of anesthesia
- Highest numerical rating score for pain (NRS – a linear 11 point scale for self-reported pain) during admission in the recovery room
- Mean cumulative intravenous opioid dose administered during admission in the recovery room – converted to morphine equivalent dose (MEQ)
- Occurrence of postoperative nausea and vomiting in the recovery room requiring anti-emetics
- Patient satisfaction on a scale of 0 (extremely unsatisfied) to 10 (extremely satisfied)
- Anxiety Trait scored by Spielberger's State Anxiety Inventory (STAI-T) at baseline
- General anxiety scored by the anxiety subscale of the Hospital Anxiety and Depression Scale (HADS-A) at baseline

#### 8.1.3 Other study parameters

##### *Procedure related*

- Patient participation to the daily pre-operative practice of Slow PACE breathing

##### *Baseline and surgery parameters*

- Age
- Length and weight
- American Society of Anesthesiologists classification (ASA class)
- Sociodemographic status (household, marital state, employment, education)
- Intoxications
- History of sedative or anti-depressive medication use
- Type of breast cancer and type of breast cancer surgery
- Underlying disease(s)

*Intraoperative*

- The following vital signs are scored at baseline (e.g. measured on the outpatient department), at arrival on the operation room, just before induction and at the first measurement after induction:
  - Systolic-, diastolic-, and mean blood pressure (mmHg)
  - Heart rate (beats per minute)
  - Oxygen saturation (SpO2 in %)
  - Respiratory rate (breaths per minute)
- Type and dose of anesthetic medication used for induction of anesthesia
- Type and dose of vasoactive medication used during or within five minutes after induction
- Anesthetic medication used for maintenance of anesthesia
- Type and dose of administered opioids
- Type and dose of other analgesia
- Anti-emetics used
- Perioperative anesthesiological management regarding locoregional techniques
- Duration of anesthesia
- Duration of surgery

*Postoperative - recovery room*

- Vital signs
- Highest NRS during admission in the recovery room
- Mean cumulative intravenous opioid dose administered during admission in the recovery room (MEQ)
- Postoperative nausea or vomiting (Y/N)

**8.2 Randomisation, blinding and treatment allocation***Randomisation*

Patients will be randomly allocated to the study arms (usual care or Slow PACE breathing) using blocked randomization with age (<50 versus ≥50) as randomisation stratification factor in Castor.

*Blinding*

In this trial it is not possible to blind the patient or the investigators.

## 8.3 Study procedures

### 8.3.1 General

To benefit patient comfort and because our easy-to-learn intervention is very low risk and low burden, we aim to provide all contact for this study online, supported by additional contact by (video)phone. We also aim to obtain informed consent digitally (see §11.2). We want to prevent unnecessary visits to the hospital just for the study, because many breast surgery patients do not live nearby the Antoni van Leeuwenhoekziekenhuis.

### 8.3.2 Measures of anxiety

#### *Baseline (T0)*

After obtaining informed consent participants will fill out the baseline questionnaires online: STAI and HADS-A.

Spielberger's State-Trait Anxiety Inventory (STAI) is a well validated and widely used method of measuring an individual's temperament or normal anxiety levels (Trait Anxiety) as well as their current or situational anxiety levels (State Anxiety). Each scale is comprised of 20 statements. The participant scores each question on a 4-point scale ranging from 1 (not at all) to 4 (very much so), with the total score ranging from 20 to 80. Higher scores indicate higher levels of anxiety symptoms. A cut-off score of 40 is commonly used to define probable clinical levels of anxiety. In this study, we will ask participants to complete both Trait and State subscales at baseline. The STAI-T will give an estimation of patients at high risk for anxiety.

Besides the STAI-T we will also take the HADS-A subscale at baseline to identify breast cancer patients with high anxiety levels. The Hospital Anxiety and Depression Scale is a questionnaire that has been found to be a reliable instrument for detecting states of anxiety and depression in a hospital setting. The HADS-A is the anxiety subscale that consists of seven items. Each item is rated on a 4-point scale (ranging from 0 = no not at all, to 3 = yes definitely), for a total score ranging from 0 to 21. A subscale score above 8 denotes anxiety.

The HADS-A is a shorter questionnaire than STAI-T and is used more commonly in the Antoni van Leeuwenhoekziekenhuis to measure general anxiety. We will compare STAI-T to HADS-A in prediction of high general anxiety.

### *Pre-operative (T1)*

On the day of surgery the participant will be asked complete the STAI-S questionnaire just before surgery on the iPad provided by the investigator.

### *Post-operative (T2)*

Post-operatively the participant will be asked complete the STAI-S questionnaire online again. The participant will also be asked to score patient satisfaction on a scale of 0 (extremely unsatisfied) tot 10 (extremely satisfied).

## **8.3.3 Slow PACE breathing**

### *Training*

After completion of the baseline questionnaires, participants randomized in the intervention group will receive a link to the study site with a comprehensive instruction video explaining the Slow PACE breathing technique. Furthermore a 'kick-off' video-call is planned with an investigator to give additional instructions and to answer any questions regarding the breathing technique.

After the initial instructions participants are asked to practice Slow PACE breathing daily for at least 5 minutes, guided by an audio-guide to guide the breathing to a frequency of 6 breaths per minute (0.1 Hz). This audio-file will be available on the site.

The participant will receive the researcher's contact details, so she can always reach us in case of further questions or need for guidance.

### *Pre-operative*

On the day of surgery, the participant will be transported to the operating room, where iv access is obtained and the participant is monitored by electrocardiogram, and pulse oximetry and non-invasive blood pressure will be measure by a cuff every 2-3 minutes (as is the normal procedure). The blood pressure at arrival on the operation will be noted (BP 0).

After the 'time-out procedure' the participant randomized in the intervention group will be asked to start with the Slow PACE breathing technique. This will be guided by the same audio-fragment provided during the training, so the participant has a recognizable breath pacer. The blood pressure (BP 1) and the respiratory rate at the start of induction will be noted in both groups.

### 8.3.4 Other study procedures

#### *Preoperative*

To monitor participation to the daily training sessions, participants in the intervention group will receive a daily email with a reminder and a link to the electronic CRF (Castor), in which they can score if they had time to practice the slow-paced breathing the day before (Y/N).

#### *Intra-operative*

Intra-operatively care as usual will be given to all patients. Anesthesia is induced with sufentanil and propofol. The blood pressure directly after induction will be noted (BP 2). Anesthesia is maintained by propofol or sevoflurane at the discretion of the attending anesthetist. Depth on anesthesia will be monitored by the Bispectral index (BIS)-monitor and kept between 40 to 60. Routine general anesthesia, perioperative pain management, anti-emetic prophylaxis and fluid management will be performed and given in the intraoperative and postoperative period according to routine clinical use. Once anesthesia is terminated, patients are transported to the recovery room.

#### *Postoperative*

In the recovery room care as usual will be given to all patients. The patient's respiratory rate, SpO2 and heart rate are measured continuously and a non-invasive blood pressure is measured at least every 15 minutes. Recovery room nurses are aware of the study protocol, but unaware of treatment allocation.

[figure not shown]
On arrival, the patient is asked to rate their pain on the 11 point Numerical Rating Scale and is asked whether they require any further pain relief. They are also asked for nausea.

All medications given and all pain scores and postoperative nausea or vomiting are noted in the electronic patient record. At least 2 NRS scores are noted for every patient (one on arrival and one before discharge).

#### *End of study period*

Data acquisition ends after completion of the post-operative questionnaire (STAI-S) and scoring of patient satisfaction.

Study flowchart

#### 8.4 Withdrawal of individual subjects

Subjects can leave the study at any time for any reason if they wish to do so without any consequences. The subject can either email or call the researcher on the provided email or phone number at any time to inform the researcher. The investigator can decide to withdraw a subject from the study for urgent medical reasons.

#### 8.5 Replacement of individual subjects after withdrawal

Subjects withdrawing consent before any data are collected will be replaced.

#### 8.6 Follow-up of subjects withdrawn from treatment

Patients who are withdrawn by their physician will be subjected to the same follow up as per the study protocol. When a patient withdraws their consent they will not be subjected to follow-up.

#### 8.7 Premature termination of the study

In case the study is ended prematurely, the investigator will notify the accredited METC within 15 days, including the reasons for the premature termination. Reasons for premature termination could be a slow inclusion rate.

### 9. SAFETY REPORTING

#### 9.1 Temporary halt for reasons of subject safety

In accordance to section 10, subsection 4, of the WMO, the sponsor will suspend the study if there is sufficient ground that continuation of the study will jeopardise subject health or safety. The sponsor will notify the accredited METC without undue delay of a temporary halt including the reason for such an action. The study will be suspended pending a further positive decision by the accredited METC. The investigator will take care that all subjects are kept informed.

## 9.2 AEs, SAEs and SUSARs

### 9.2.1 Adverse events (AEs)

Adverse events are defined as any undesirable experience occurring to a subject during the study, whether or not considered related to trial procedure. All adverse events reported spontaneously by the subject or observed by the investigator or his staff will be recorded.

The investigator will report all AEs to the sponsor without undue delay after obtaining knowledge of the events, except for the following AEs:

- AEs that are a result of the surgical procedure

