**Feasibility analysis**

After inclusion of 30 patients, we plan to assess the compliance to Slow PACE breathing just before induction. A failure to compliance is when a patient in the intervention group does not perform the guided Slow PACE breathing at induction of anesthesia, defined as breathing at rate of  $\geq 10$  breaths per minute. Assuming 95% patients will comply, the lower limit of a binomial exact 95% confidence interval for the compliance rate will be 80%. If the lower limit of the 95% confidence interval for the compliance rate is below 80%, then additional strategies will be deployed to ensure patients adhere to the training of the breathing technique (e.g. weekly calls to check-up and remind the patients) and patients with failure to compliance will be reviewed for point of improvement to increase compliance.

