### 11.2 Recruitment and consent

#### 11.2.1 Recruitment

Patients will be screened for eligibility during the routine preoperative consultation. Should a patient be eligible, then she will be contacted by one of the researchers by phone to receive oral information about the study. This contact will take place at least 2 weeks prior to the surgical procedure.

Many patients in this population live far from the hospital and do not frequently visit the Antoni van Leeuwenhoek hospital in person. If receiving neoadjuvant treatment, they often receive this in a hospital near their home address. To benefit patient comfort and because our easy-to-learn intervention is very low risk and low burden, we aim to provide all contact for this study online, supported by additional contact by (video)phone. We used the 'Handreiking elektronische toestemmingsverlening voor deelname aan medisch-wetenschappelijk onderzoek, 22 augustus 2022' and the 'Checklist METC NedMec eConsent (NL) version 1 jan 2023' provided by the Centrale Commissie Mensgebonden Onderzoek (CCMO) to ensure compliance with article 6 lid 2 WMO.

If a patient is interested in participation, the document with the patient information and informed consent form will be sent digitally in an attachment by email using Zivver. Zivver is a service used in the AvL to send and receive information securely between patients and doctors in end-to-end encrypted emails protected by a personal password. Only the sender and the recipient can open the email and access the attached files. Zivver nor the IT department has access to the personal password, nor to the decryption key. This means that nobody but the sender and the recipient of the message can decrypt the message and read its content. Zivver complies with the concerning privacy and information protection regulations, like GDPR.

In Zivver the researcher can audit if the email has been received and opened by the recipient. The IT department has access to the audit-logs in which they can audit when

and where the email has been accessed and if any settings have been changed, without having access to the content of the email.

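### Adverse events are captured only if volunteered or observed while contact differs by arm, and the daily practice item cannot separate discomfort from lack of time

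*Combined protocol and SAP*

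**What the plan says.** Section 9.2.1 defines adverse events broadly: "Adverse events are defined as any undesirable experience occurring to a subject during the study, whether or not considered related to trial procedure". It then sets the capture method: "All adverse events reported spontaneously by the subject or observed by the investigator or his staff will be recorded". One category is exempt from reporting to the sponsor: "AEs that are a result of the surgical procedure".

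Section 8.3.2 describes the STAI-S at T1, and the STAI-S plus a satisfaction score at T2. Neither is described as including a question on complaints.

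For the intervention arm, Section 8.3.3 adds: "Furthermore a 'kick-off' video-call is planned with an investigator to give additional instructions and to answer any questions regarding the breathing technique". Under the same training heading the participant receives contact details, "so she can always reach us in case of further questions or need for guidance". Section 8.3.4 gives this arm a daily reminder e-mail with a link to the eCRF, "in which they can score if they had time to practice the slow-paced breathing the day before (Y/N").

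On timing, Section 11.2.1 says of the recruitment call: "This contact will take place at least 2 weeks prior to the surgical procedure". Section 11.2.2 allows at least 48 hours for the decision.

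Section 4.4 plans a feasibility check after 30 inclusions, based on breathing rate at induction. If the lower confidence limit for compliance is below 80%, "additional strategies will be deployed to ensure patients adhere to the training of the breathing technique (e.g. weekly calls to check-up and remind the patients"). In addition, the non-compliant patients are reviewed individually.

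Section 8.2 states that neither patients nor investigators can be blinded. Sections 10.3 to 10.5 contain no adverse event summary or comparison.

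**The concern.** Most of the exposure to the intervention is unsupervised practice at home. Unsolicited capture depends on how readily a participant thinks to report something and has someone to report it to. In this open-label design the reminders and the link to the study team are built into one arm only, so the chance that an event is recorded may depend on the arm.

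The one instrument in use during that period asks about time, not tolerance. If some women stop because the breathing makes them uncomfortable or more anxious, the form as described does not show it.

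At stake are the protocol's own statements that the intervention carries no physical risk (Summary), adds no risk and so needs no DSMB (Section 9.5), and poses negligible risk (Section 11.4). Data collected this way could neither support nor question them well, and complaints that were never elicited cannot be recovered when the final report is written.

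**Working it through.** **1. Figure to reproduce.** The plan states no adverse event rate, capture rate or safety comparison, so there is no figure of its own to check on this point.

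**2. Contact and instruments by arm, from randomisation to T2.**

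| Element (section) | Intervention | Control | Question on complaints described? |
|---|---|---|---|
| Kick-off video-call (8.3.3) | Yes | No | No; instruction and questions on the technique |
| Daily e-mail and eCRF item (8.3.4) | Yes | No | No; yes/no on time to practise |
| Contact details for guidance (8.3.3) | Yes | Not described here | No; patient must initiate |
| E-mail or phone route, described for withdrawal (8.4) | Yes | Yes | No; patient must initiate |
| T1 form (8.3.2) | Yes | Yes | No |
| Recovery-room pain, nausea and vomiting, medication (8.3.4) | Yes | Yes | Pain and nausea are asked of every patient |
| T2 form (8.3.2) | Yes | Yes | No |

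The arms differ in the first three rows, all before surgery. Only the recovery room has systematic elicitation, and it is the same in both arms.

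**3. Length of the period.** If the recruitment call falls exactly 14 days before surgery and the 48-hour minimum is used, 14 − 2 = 12 days at most remain for consent, baseline questionnaires, instruction and practice. The period is longer if the call is earlier. Supervised performance is the single occasion at induction.

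**4. Effect of unequal capture.** Let n be patients per arm, p the true event risk (the same in both arms), and s_I and s_C the capture probabilities in the intervention and control arms.

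- Expected recorded events: n × p × s_I and n × p × s_C.
- Apparent ratio: (n × p × s_I) / (n × p × s_C) = s_I / s_C.

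The true risk cancels, so the apparent ratio is only the ratio of the capture probabilities, which the documents do not give. For illustration, take n = 79 (Section 4.4) and assume p = 20%, s_C = 50% and s_I from 50% to 80%:

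- s_C = 50%: 79 × 0.20 × 0.50 = 7.9 events
- s_I = 60%: 79 × 0.20 × 0.60 = 9.5 events, ratio 1.2
- s_I = 80%: 79 × 0.20 × 0.80 = 12.6 events, ratio 1.6
- s_I = 50%: ratio 1.0

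At p = 10% or 30% the ratios are the same. This shows the mechanism; it does not estimate the bias.

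**5. What the daily item can identify.** The proportion answering no is P(no time) + P(discomfort) + P(other reason). One observed proportion cannot be split into three parts. Only a volunteered report, recorded separately under Section 9.2.1, would reveal the second.

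**6. At induction.** Sections 1.3 and 4.4 class a patient who does not perform the technique as non-compliant. The criterion is a breathing rate of at least 10 per minute, and no reason category is described. Section 10.2 then removes her from the per-protocol set.

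**The case against.** The case on the other side has several sound parts.

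- **No comparison is planned.** Safety is not an objective in Section 2, and Section 10 contains no adverse event analysis. This stands: no specified test is biased, and the effect is on later statements only.
- **The extra contact may yield few events.** The kick-off call comes before daily practice starts, the e-mails carry no question on complaints, and the weekly calls are a contingent example. This also stands. Counting every e-mail as an opportunity for capture would exaggerate the difference between arms.
- **Other routes exist.** All participants can e-mail or phone the researcher (Section 8.4), and recovery-room nurses, who are unaware of allocation, record pain and nausea in both arms. The first route still depends on volunteering; the second begins after home practice has ended.
- **Light capture is a defensible choice** for a short breathing exercise in patients screened for severe lung disease. That bears on priority, but it does not give the daily item the ability to show intolerance.

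Three stronger readings are tempting and not supported. A reader might infer that intolerance is recorded as lack of time. However, volunteered intolerance meets the adverse event definition and would be recorded as such, and the eCRF is only paraphrased in the protocol. A reader might infer that the Section 4.4 check acts on the daily answers and responds only with reminders. In fact it uses breathing rate at induction, includes a case review, and concerns patients whose home practice is already over. A reader might also infer a known inflation of events in the intervention arm, but neither its size nor its existence can be established from the documents.

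**Conclusion.** The point holds as a limitation of data capture. Unsolicited recording combined with unequal contact in an open-label trial leaves room for ascertainment to differ by arm during home practice. The daily item, as described, cannot distinguish discomfort from lack of time unless the participant volunteers it.

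The size is unknown; the ratios of 1.0 to 1.6 above follow entirely from assumed capture probabilities. Randomisation, sample size, the STAI-S model and the listed secondary tests are unaffected. What suffers is any statement on tolerability or safety in the final report or publication.

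The conclusion assumes that the eCRF contains no reason or symptom field beyond what Section 8.3.4 describes, and that the T1 and T2 forms contain no complaint question beyond Section 8.3.2. If either is present, the corresponding part of the point falls away. The change is worth making because it is cheap and the information cannot be collected afterwards.

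**What to change.** 1. **Daily form (Section 8.3.4).** Replace the yes/no item with *practised / not practised: no time / not practised: discomfort or felt worse / other*. Pass discomfort answers to the investigator for recording under Section 9.2.1.
2. **Both arms (Section 8.3.2).** Put the same short question on new complaints or discomfort after the STAI-S, so that it cannot influence the score. Ask it at T1, covering the period since joining the study, and at T2 if wanted, with surgical complaints flagged separately. State in Section 10 that solicited and spontaneous adverse events will be reported by arm in separate tables.
3. **Feasibility review (Section 4.4).** In the case review of patients who do not comply at induction, record the reason, with discomfort as one category.

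**Cost.** A changed answer list on one existing form, one question on one or two existing questionnaires, and one field in a review already planned. No visits are added and the sample size does not change. More minor events will need logging. A T2 question would bring in surgical complaints, which Section 9.2.1 exempts from reporting to the sponsor but not from recording. The same question in both arms equalises the opportunity to report, but the answers still come from unblinded patients, so a by-arm comparison would remain descriptive.
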